## 7. RATIONALE AND BACKGROUND

Coronavirus disease 2019 (COVID-19), caused by severe acute respiratory syndrome coronavirus 2 (SARS-CoV-2), was declared a global pandemic by the World Health Organization (WHO) on 11 March 2020^6, and continues to be a serious global threat to public health and to health care systems. As of 07 March 2022, COVID-19 has infected at least 446 million people, and has led to at least 6 million deaths worldwide.

In order to prevent SARS-CoV-2 infection, several COVID-19 vaccines have been approved or authorized for emergency use by Health Authorities and are being administered globally.

In December 2021, the Food and Drug Administration (FDA) granted emergency use authorization (EUA) for a 5 day course of treatment for 2 separate oral antiviral agents, nirmatrelvir/ritonavir and molnupiravir, for the treatment of COVID-19 in adult and pediatric patients 12 years of age and older who weigh at least 40 kg, with mild to moderate COVID-19 who are at high risk for progressing to severe illness. In January 2022, remdesivir received approval for this same population. This treatment is administered by IV infusion over 3 days for nonhospitalized patients with mild to moderate COVID-19 who are at high risk for progressing to severe illness.

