### **Primary Objectives:**

**Objective 1:** To estimate viral SARS-CoV-2 rebound rates (primary definition: 1. a positive test (at the index date), followed by a single negative test, followed by a positive test - within 28 days, or 2. 1 or more positive tests at the index date, followed by 1 or more negative tests, followed by a positive test within same 28 day time span), prior to the Omicron era and during the Omicron era (defined as 01 December 2021 to present), in high frequency (volume) SARS-CoV-2 diagnostic testers (primary definition: 1 or more positive tests followed by 1 or more negative tests followed by 1 or more positives within same 28 day time span and median time between tests (positive or negative) is at most 10 days).

**Objective 2:** To estimate viral SARS-CoV-2 rebound rates (using the primary definition of viral SARS-CoV-2 rebound), prior to the Omicron era and during the Omicron era, in high frequency (volume) SARS-CoV-2 diagnostic testers (using the primary definition of high frequency testing), among those treated with Paxlovid/nirmatrelvir-ritonavir for SARS-CoV-2 versus those with no evidence of SARS-CoV-2 treatment (untreated for SARS-CoV-2), stratified by:

- a. Demographics of participants
- b. Time from first positive test to treatment (if treated).
- c. Participants at high-risk for progression to severe SARS-CoV-2 versus those not at high-risk, if sample size allows. If sample size is limited, age (<50 years of age versus 50+ years of age) will be used as a proxy for high-risk for progression to severe SARS-CoV-2 status)

- d. Co-infections
- e. Vaccinated against SARS-CoV-2 (has received at least 1 dose) and time since last vaccine dose > 6 months vs. ≤6 months
- f. Multiple SARS-CoV-2 treatment prescription status

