### **9.2.2. Time periods**

#### **9.2.2.1. Study period**

The study will include an overall study period of June 01, 2020, to February 28, 2023.

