#### **9.2.2.3. Index date**

Index date is defined as first confirmed positive SARS-CoV-2 rRT-PCR test within a positive - negative – positive test sequence that occurs within 28 days during the study period (by omicron era status). Only the first infection for each patient during the study period (by omicron era status) will be examined.

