## 9.8. Data analysis

Descriptive statistics among individuals with SARS-CoV-2 in the Helix Respiratory Registry that overlap with the retrospective Komodo Healthcare claims data will be summarized. Means with standard deviations, medians with interquartile ranges will be provided for continuous variables. Numbers and percentages will be provided for dichotomous variables or categorical variables.

For exploratory analyses, logistic regression or Cox proportional hazards regression models will be used to identify risk factors and outcomes for viral SARS-CoV-2 rebound in adjusted analyses. Model selection will balance biological and contextual knowledge for potential confounders with statistical considerations for model fit and the bias versus variance tradeoff.

An analysis comparing viral SARS-CoV-2 rebound, between participants treated with Paxlovid, untreated participants (and pending sufficient sample size, comparator SARS-CoV-2 treatment group(s) described above) will be conducted. Viral SARS-CoV-2 rebound and other outcomes in participants who received Paxlovid compared with untreated participants (and/or comparator SARS-CoV-2 treatment group(s), pending sufficient sample size) will be evaluated using multivariable Cox regression models with propensity score inverse probability of treatment weighting (IPTW) with a robust variance estimator having age, sex, week and year of initial positive SARS-CoV-2 test, and potentially the aforementioned baseline clinical characteristics and comorbidities as independent variables to account for time-varying confounding. Standardized mean differences (SMDs) will be calculated to check whether IPTW yielded comparable cohorts, considering an SMD below 0.1 as indicating satisfactory covariate balance.

Detailed methodology for summary and statistical analyses of data collected in this study will be documented in a statistical analysis plan (SAP), which will be dated, filed, and maintained by the sponsor. The SAP may modify the plans outlined in the protocol; any major modifications of primary endpoint definitions or their analyses would be reflected in a protocol amendment.

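### Treated-versus-untreated rebound is requested for an era that ended before Paxlovid was authorised, and the IPTW comparison in Section 9.8 has no calendar window

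*Supplement*

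**What the plan says.** - **Eras.** Primary Objective 1 (Section 8) splits the estimates "prior to the Omicron era and during the Omicron era (defined as 01 December 2021 to present"). Section 9.2.2.1 states: "The study will include an overall study period of June 01, 2020, to February 28, 2023".
- **Contrast.** Primary Objective 2 keeps the era split and compares rebound "among those treated with Paxlovid/nirmatrelvir-ritonavir for SARS-CoV-2 versus those with no evidence of SARS-CoV-2 treatment (untreated for SARS-CoV-2), stratified by" six factors, a to f. Secondary Objectives 1-3 and Exploratory Objectives 1-2 request the treated-versus-untreated comparison in both eras too. The abstract in Annex 1 repeats the primary and secondary objectives.
- **Infection selected.** Section 9.2.2.3: "Only the first infection for each patient during the study period (by omicron era status) will be examined".
- **Authorisation.** Section 7: "In December 2021, the Food and Drug Administration (FDA) granted emergency use authorization (EUA") for nirmatrelvir/ritonavir, for patients aged 12 or over "with mild to moderate COVID-19 who are at high risk for progressing to severe illness". The day in December is not given.
- **Weighted comparison.** Section 9.8 plans Cox models with IPTW, "having age, sex, week and year of initial positive SARS-CoV-2 test". Clinical characteristics and comorbidities are optional additions. Balance is judged by an SMD below 0.1. The section does not say whether the model is pooled or fitted by era, which weights are used, or which index dates enter.
- **Risk status.** Section 9.3.2 has no exclusions. Risk is a stratifier: "Participants at high-risk for progression to severe SARS-CoV-2 versus those not at high-risk, if sample size allows", with age below or above 50 as the fallback.

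**The concern.** The dates in Sections 7 and 8 conflict. The pre-Omicron era closes on 30 November 2021 and the drug is first authorised in the following month. A primary objective, all three secondary objectives and both exploratory objectives therefore request a comparison for a period in which one arm could not normally exist.

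The same gap reaches the weighted analysis. Calendar week and year are in the model, and the probability of treatment is zero in every week before authorisation. If those weeks enter a pooled model, the untreated group includes infections from an earlier variant era with no treated infections to set against them. A difference in rebound between the groups could then reflect era (variant, vaccination, testing habits) rather than treatment, in a post-authorisation safety study where this comparison is a central result.

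A related, weaker issue is that the EUA covers high-risk patients only. Risk status is then a main determinant of treatment, yet the propensity model need not contain it.

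**Working it through.** The plan states no sample size, power or expected treated count, so there is no figure of its own to reproduce. The check is date arithmetic followed by a balance calculation.

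**1. Calendar span**

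- Study period, 01 June 2020 to 28 February 2023: 1,003 days.
- Pre-Omicron, 01 June 2020 to 30 November 2021: 548 days; 548/1,003 = 54.6%.
- Omicron era: 1,003 − 548 = 455 days.
- Since the EUA may fall up to 30 days after 01 December, the period with authorised drug is between 455 − 30 = 425 and 455 days.
- Days with authorised Paxlovid before 01 December 2021: 0.

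The treated cell is empty whatever the number of infections. The only exceptions would be late-November index dates with dispensing after authorisation (Section 9.4 counts treatment on or after index), or use before authorisation. Neither would give a usable group.

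**2. What can and cannot be estimated under Primary Objective 2**

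| | Untreated | Treated | Contrast |
|---|---|---|---|
| Pre-Omicron | yes, in strata that apply to untreated patients | effectively empty | no |
| Omicron | yes | yes, after the EUA | yes, after the EUA |

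Stratum b, time from first positive test to treatment, exists only for treated patients, so it is wholly empty before Omicron.

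**3. The IPTW model under each reading of Section 9.8**

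- *By era.* The pre-Omicron model has no treated patients and cannot be fitted.
- *Omicron only.* The era problem disappears, apart from at most 30 days in December 2021.
- *Pooled, average-effect weights.* A pre-EUA untreated patient has propensity e = 0 and weight 1/(1 − 0) = 1, and so stays in the comparison. No treated patient exists to be weighted up as a counterpart.
- *Pooled, treated-population weights.* The same patient has weight e/(1 − e) = 0 and drops out.

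**4. Size of the imbalance in the pooled, average-effect case**

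Let f be the share of infections that are pre-Omicron. After weighting, the pre-Omicron share is 0 among the treated and f among the untreated, so

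SMD = f / √[f(1 − f)/2] = √[2f/(1 − f)].

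The documents do not give f. Section 9.6 reports 21,991 infections among high-frequency testers without an era split. In the feasibility window (10 October 2020 to 10 August 2022), 417 of 670 days, or 62%, are pre-Omicron. I assume f from 10% to 62%.

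| Assumed f | SMD |
|---|---|
| 10% | 0.47 |
| 30% | 0.93 |
| 50% | 1.41 |
| 62% | 1.81 |

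Meeting the 0.1 limit needs 2f/(1 − f) < 0.01, that is f < 0.01/2.01 = 0.5%.

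**5. Risk status within the Omicron era (illustration only)**

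The documents give no treatment rates. Assume half of the 21,991 infections fall in this era (10,995.5), 50% are high-risk, 20% of those are treated, and 0.5% of the rest are treated. Treated: 1,099.55 high-risk at weight 5 and 27.49 others at weight 200. Effective treated sample = (Σw)²/Σw² = 10,995.5²/(27,489 + 1,099,550) = 107, from 1,127 treated. Over 30-70% high-risk, 5-20% of them treated and 0.5-2% of the rest treated, the effective sample ranges from about 10% to 84% of the treated count. This shows why overlap should be reported. It is not a prediction.

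**The case against.** The strongest reply is that the positivity problem depends on a pooled model. Every comparative objective is split by era and the index infection is chosen by era, so an era-specific fit is at least as natural a reading. Untreated patients with zero propensity also do not produce infinite weights. They carry weight 1, or weight 0 if the treated population is the target. Weight type, trimming and overlap rules are commonly left to the SAP, which is not shown. The study is described as descriptive, and an empty treated column would show as n = 0 without biasing the Omicron-era rates.

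Most of this stands, and it limits the point. A reader might infer more than the documents support in four ways:

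- *That IPTW positivity certainly fails.* It fails under pooling with average-effect weights. Section 9.8 commits to neither.
- *That half of the Primary Objective 2 tables cannot be filled.* Only the pre-Omicron treated cells and the contrast are lost.
- *That 55% of the data are affected.* The 55% is calendar days. Infections are not split by era.
- *That the comparison must be restricted to the high-risk list in Section 9.3.1.* That list is described as resembling the EPIC-HR criteria, not as the EUA definition, and Section 9.10 admits incomplete similarity even to EPIC-HR. Restriction could drop treated patients whom the list misses, and it changes the target population. A near-zero treatment probability in other patients is inferred from the EUA wording, not from a count; off-label use or comorbidities missed in claims may leave some treated patients there.

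The reply does not rescue the pre-Omicron contrast. The contrast is written into the protocol's objectives, and Section 9.8 itself says major modifications of primary endpoint definitions or their analyses would go into a protocol amendment.

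**Conclusion.** The point holds in two parts of different strength.

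**Firm.** On the protocol's own dates, the pre-Omicron treated cells and the treated-versus-untreated contrast are effectively empty in Primary Objective 2, Secondary Objectives 1-3 and Exploratory Objectives 1-2. This covers 548 of 1,003 study days and rests on no assumption beyond negligible use before authorisation.

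**Conditional.** Section 9.8 leaves the calendar window of the IPTW comparison open. Fitted by era, the pre-Omicron model is inestimable. Pooled with average-effect weights, calendar time cannot meet the plan's SMD limit unless fewer than about 0.5% of infections are pre-Omicron, and treatment is confounded with era. An Omicron-only fit or treated-population weights would largely avoid this.

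The risk-status issue supports requiring those covariates and checking overlap. It does not establish that treated cells outside the high-risk group are empty.

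**What to change.** In Sections 8 and 9.8 and in the abstract:

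1. Limit every treated-versus-untreated estimate, and the IPTW model, to index dates on or after the EUA date, and state that date.
2. Report the pre-Omicron era descriptively only: the overall rate under Primary Objective 1 and the untreated rates by those strata that apply to untreated patients.
3. Make the high-risk characteristics required terms in the propensity model, and report propensity overlap by treatment group alongside the SMDs.
4. Add restriction to the Section 9.3.1 high-risk list as a sensitivity analysis.

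**Cost.** A change of wording and a date filter. The comparison keeps 425 to 455 of the 1,003 study days and loses untreated patients, none of whom had a treated counterpart in calendar time. Any late-November index case dispensed Paxlovid after authorisation would also drop out. The number of infections remaining cannot be given, because the 21,991 is not split by era.

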**Secondary Objectives:**

**Objective 1:** As a sensitivity analysis, using an alternate less strict definition of high frequency (volume) SARS-CoV-2 diagnostic tester (defined as tested for SARS-CoV-2 at least 3 times and median time between tests (positive or negative) is at most 14 days), to estimate viral SARS-CoV-2 rebound rates (using the primary definition), prior to the Omicron era and during the Omicron era, in high frequency (volume) SARS-CoV-2 diagnostic testers, among those treated with Paxlovid/nirmatrelvir-ritonavir for SARS-CoV-2 versus those with no evidence of SARS-CoV-2 treatment (untreated) for SARS-CoV-2, stratified by:

- a. Demographics of participants
- b. Time from first positive test to treatment (if treated).
- c. Participants at high-risk for progression to severe SARS-CoV-2 versus those not at high-risk, if sample size allows. If sample size is limited, age (<50 years of age versus 50+ years of age) will be used as a proxy for high-risk for progression to severe SARS-CoV-2 status)
- d. Co-infections
- e. Vaccinated against SARS-CoV-2 (has received at least 1 dose) and time since last vaccine dose >6 months vs. ≤6 months
- f. Multiple SARS-CoV-2 treatment prescription status

**Objective 2:** As a sensitivity analysis, using an alternate stricter definition of high frequency (volume) SARS-CoV-2 diagnostic tester (defined as tested for SARS-CoV-2 at least 3 times and median time between tests (positive or negative) is at most 7 days), to estimate viral SARS-CoV-2 rebound rates (using the primary definition), prior to the Omicron era and during the Omicron era, in high frequency (volume) SARS-CoV-2 diagnostic testers, among those treated with Paxlovid/nirmatrelvir-ritonavir for SARS-CoV-2 versus those with no evidence of SARS-CoV-2 treatment (untreated) for SARS-CoV-2, stratified by:

- a. Demographics of participants
- b. Time from first positive test to treatment (if treated).

- c. Participants at high-risk for progression to severe SARS-CoV-2 versus those not at high-risk, if sample size allows. If sample size is limited, age (<50 years of age versus 50+ years of age) will be used as a proxy for high-risk for progression to severe SARS-CoV-2 status)
- d. Co-infections
- e. Vaccinated against SARS-CoV-2 (has received at least 1 dose) and time since last vaccine dose >6 months vs. ≤6 months
- f. Multiple SARS-CoV-2 treatment prescription status

**Objective 3:** As a sensitivity analysis, under a less strict definition of viral SARS-CoV-2 rebound (defined as two positives more than 14 days apart), to estimate viral SARS-CoV-2 rebound rates, prior to the Omicron era and during the Omicron era, in high frequency (volume) SARS-CoV-2 diagnostic testers (using the primary definition), among those treated with Paxlovid/nirmatrelvir-ritonavir for SARS-CoV-2 versus those with no evidence of SARS-CoV-2 treatment (untreated) for SARS-CoV-2, stratified by:

- a. Demographics of participants
- b. Time from first positive test to treatment (if treated).
- c. Participants at high-risk for progression to severe SARS-CoV-2 versus those not at high-risk, if sample size allows. If sample size is limited, age (<50 years of age versus 50+ years of age) will be used as a proxy for high-risk for progression to severe SARS-CoV-2 status)
- d. Co-infections
- e. Vaccinated against SARS-CoV-2 (has received at least 1 dose) and time since last vaccine dose >6 months vs. ≤6 months
- f. Multiple SARS-CoV-2 treatment prescription status

**Exploratory Objectives:**

**Objective 1:** To estimate viral SARS-CoV-2 rebound rates (using the primary definition of viral SARS-CoV-2 rebound), prior to the Omicron era and during the Omicron era, in high frequency (volume) SARS-CoV-2 diagnostic testers (using the primary definition of high frequency testing), among those treated with Paxlovid/nirmatrelvir-ritonavir for SARS-CoV-2 versus those with no evidence of SARS-CoV-2 treatment (untreated) for SARS-CoV-2, stratified by:

- a. Demographics of participants
- b. Time from first positive test to treatment (if treated).

- c. Participants at high-risk for progression to severe SARS-CoV-2 versus those not at high-risk, if sample size allows. If sample size is limited, age (<50 years of age versus 50+ years of age) will be used as a proxy for high-risk for progression to severe SARS-CoV-2 status)
- d. Co-infections
- e. Vaccinated against SARS-CoV-2 (has received at least 1 dose) and time since last vaccine dose > 6 months vs. ≤ 6 months
- f. Multiple SARS-CoV-2 treatment prescription status

**Objective 2:** To examine risk factors and clinical outcomes of viral SARS-CoV-2 rebounders (using the primary definition of viral SARS-CoV-2 rebound), prior to the Omicron era and during the Omicron era in high frequency (volume) SARS-CoV-2 diagnostic testers (using the primary definition of high frequency testing), among those treated with Paxlovid/nirmatrelvir-ritonavir for SARS-CoV-2, those untreated for SARS-CoV-2 versus those with no evidence of SARS-CoV-2 treatment (untreated) for SARS-CoV-2, as defined below:

- a. Risk factors
  - i. High-risk factors
  - ii. Demographics
  - iii. Other risk factors to be determined
- b. Clinical outcomes, based on healthcare utilization during follow-up post-index date
  - i. Hospitalization (including length of stay)
  - ii. Hospitalizations with invasive mechanical ventilation
  - iii. Emergency room visits
  - iv. Urgent care visits
  - v. All-cause mortality

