#### **9.2.2.4. Follow-up**

The follow-up period starts at index date and participants will be followed until the date of the first occurring of the following events:

- Death
- At the end of their database disenrollment from the database
- At the end of study period
- Occurrence of the outcome/endpoint of interest

Further details will be defined in SAP.

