## Endpoints

The following are the primary endpoint:

- Viral SARS-CoV-2 rebound\*, where the main definition defines rebound as 1.) a positive test (at the index date), followed by a single negative test, followed by a positive test - within 28 days, or 2.) 1 or more positive tests starting at the index date, followed by 1 or more negative tests, followed by a positive test within same 28-day time span. Index date will be defined as first positive test date.

The following are the exploratory endpoints:

- Clinical outcomes (within 30 days of index date), based on healthcare utilization following viral SARS-CoV-2 rebound
  - Hospitalization (including length of stay)
  - Hospitalizations with invasive mechanical ventilation
  - Emergency room visits
  - Urgent care visits
  - All-cause mortality

\*Alternate definitions of viral SARS-CoV-2 rebound will be included in sensitivity analyses and detailed in the SAP.

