## Covariates

Covariates will include baseline demographic, high-risk clinical characteristics (comorbidities) for progression to severe SARS-CoV-2, medications, and health utilization, as well as those needed for the study cohort inclusion and exclusion criteria. These are not intended to be the exclusive lists. Adjustments of the covariates may be made, and additional variables may be added in SAP as needed over time. The code lists of conditions and medications (if applicable) will be provided in SAP.

*Demographics (prior to index date):*

- Age/Age group (age groups to be defined in the SAP)
- Gender
- Race/ethnicity (if available)
- Location/region (if available)

*High-risk clinical characteristics (comorbidities) for progression to severe SARS-CoV-2 (prior to index date):*

- Immunosuppressive disease or immunosuppressive treatment.
- Cancer (active) other than localized skin cancer
- Cardiovascular conditions (Cerebrovascular disease or stroke, coronary heart disease, cardiomyopathies, heart failure, etc.)
- Chronic kidney disease (CKD)
- Deyo-Charlson Comorbidity Index Score
- Diabetes mellitus
- HIV
- Hypertension

- Chronic liver disease (cirrhosis; non-alcoholic fatty liver disease; alcoholic liver disease; autoimmune hepatitis, etc.)
- Neurodevelopmental disorders
- Obesity
- Respiratory conditions (Asthma, Chronic obstructive pulmonary disease (COPD), Interstitial lung disease (ILD), Chronic lung disease, etc.)
- Sickle cell disease
- Smoking status (current or former)

*Prior healthcare characteristics (prior to index date):*

- Prior-year healthcare utilization
- Prior SARS-CoV-2 infection/s
- Prior SARS-CoV-2 vaccination/s (never vaccinated,  $\geq 1$  dose with most recent dose given within 6 months of index date,  $\geq 1$  dose with most recent dose  $>6$  months from index date)
- Prior influenza vaccinations

*Risk factors to be examined (prior to index date):*

- All demographics, high-risk clinical characteristics (comorbidities) for progression to severe SARS-CoV-2 and prior healthcare characteristics mentioned above

*Diagnostic Testing Characteristics (on or after index date):*

- High frequency (volume) SARS-CoV-2 diagnostic testing status\*\*

*Medications for treatment of COVID-19 (on or after index date):*

- Anti-SARS-CoV-2 Monoclonal Antibodies
  - Bamlanivimab/Etesevimab
  - Casirivimab/Imdevimab
  - Sotrovimab
  - Tixagevimab/Cilgavimab
  - Bebtelovimab
- Antiviral therapy
  - Paxlovid/nirmatrelvir-ritonavir

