## 9.10. Limitations of the research methods

COVID-19 is a new disease with evolving diagnostic testing, disease mechanisms and treatments. Many infected persons are thought to have mild to unrecognizable symptoms and may therefore not present for testing. Thus, participants with these infections will not be identifiable in the datasets, especially if they did not undergo repeated diagnostic testing for SARS-CoV-2. However, as high-

volume repeat testers are more likely to undergo a positive-negative-positive test pattern, which will result in an overestimate of the true proportion of participants who experience viral SARS-CoV-2 rebound (along with SARS-CoV-2 treatment rebound (including Paxlovid)) as the worst-case scenario, yet these results should form a conservative upper-limit estimate.

Participants with chronic diseases or in inpatient settings, the elderly, or other risk groups may be more likely to be under ongoing care or thought to be at higher risk and therefore may be more likely to seek care or be referred for testing. Differences among at-risk subpopulations may arise from access to care/health care seeking behaviors rather than true differences in risk. Generalizability may be limited as SARS-CoV-2 testing patterns and treatment are evolving over time, and health care seeking behaviors among participants at high-risk of SARS-CoV-2 progression may differ from those who are not at high-risk .

Additional limitations are similar to those from observational studies, including the inability to obtain detailed clinical information on disease severity and activity due to the nature of secondary databases. However, the Komodo Healthcare claims data provides a more accurate record of all prescriptions given compared to electronic health records (EHRs), which it is able to indicate whether or not a prescription is filled, including refills. Being able to access this additional component provides the opportunity to calculate additional measures (e.g., if refills were filled on time). Finally, there is a lack of complete similarity between the criteria used to construct the high-risk subcohort in this study and the high-risk criteria implemented in the EPIC-HR clinical trial.

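### The two definitions of the exploratory clinical outcomes start counting at different points; under the one that starts at index, an ER or urgent care visit at which Paxlovid was prescribed is scored as an outcome

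*Supplement*

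**What the plan says.** Section 8, Exploratory Objective 2b, lists "Clinical outcomes, based on healthcare utilization during follow-up post-index date". The list includes "Emergency room visits" and "Urgent care visits", with no restriction by reason for the visit. Section 9.2.2.4 states that "The follow-up period starts at index date", and 9.2.2.3 makes the index date the date of a positive test, not of treatment.

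The Endpoints list in 9.4 describes the same outcomes differently: "Clinical outcomes (within 30 days of index date), based on healthcare utilization following viral SARS-CoV-2 rebound".

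Under Covariates in 9.4, treatment is ascertained from the index date onward: "Medications for treatment of COVID-19 (on or after index date". Section 9.8 then plans a weighted Cox comparison of "Viral SARS-CoV-2 rebound and other outcomes in participants who received Paxlovid compared with untreated participants". The propensity score uses age, sex, week and year of the first positive test, and potentially the baseline clinical characteristics.

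The protocol does not say how the encounter that led to a prescription is handled, or encounters on the index day. Section 9.2.2.4 leaves further follow-up detail to the SAP, which is not among the documents.

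**The concern.** Paxlovid reaches the claims data through a prescription, so a treated participant needs some prescribing contact on or after the index test. An untreated participant needs none. If that contact is an ER or urgent care visit and counting starts at index, the act of becoming exposed is itself recorded as an outcome event.

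The propensity weights do not touch this. They balance what was known at baseline, and the visit arises after index as part of receiving the drug. A standardized mean difference below 0.1 on every covariate would not reveal it.

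At stake is an exploratory comparison in a study designated a post-authorization safety study (section 7). Excess ER or urgent care use among Paxlovid recipients could be misread as harm when part of it only reflects where the drug was prescribed.

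**Working it through.** **Step 1. The two start points side by side.**

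| | Exploratory Objective 2b | Endpoints, 9.4 |
|---|---|---|
| Counting starts | index date (with 9.2.2.4) | after rebound |
| Counting ends | end of follow-up | 30 days from index |
| Prescribing visit in ER or urgent care, before rebound | counted | not counted |
| Prescribing visit in ER or urgent care, after rebound | counted | counted if within 30 days of index |
| Early ER or urgent care visit of an untreated participant, before rebound | counted | not counted |

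A programmer could follow either text, and they give different event counts. The Endpoints wording keeps most prescribing visits out, but the protocol does not say that it overrides Objective 2b.

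**Step 2. Possible size under the Objective 2b wording.** The plan states no figure on this point, so there is none to reproduce. The following is illustration, and all three inputs are assumptions:

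- p = true risk of a later ER or urgent care visit, the same in both groups (no drug effect)
- f = share of treated participants whose prescribing visit was in an ER or urgent care
- g = share of untreated participants with an initial-care visit in those settings

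Taking initial and later visits as independent:

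apparent risk ratio = [f + (1 − f)p] / [g + (1 − g)p]

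With p = 5%, the treated risk is:
- f = 5%: 0.05 + 0.95 × 0.05 = 0.0975
- f = 10%: 0.10 + 0.90 × 0.05 = 0.145
- f = 20%: 0.20 + 0.80 × 0.05 = 0.24

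The untreated risk is 0.05 when g = 0. When g = f/2 it is 0.025 + 0.975 × 0.05 = 0.07375, then 0.05 + 0.95 × 0.05 = 0.0975, then 0.10 + 0.90 × 0.05 = 0.145.

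| p | f | ratio, g = 0 | ratio, g = f/2 | ratio, g = f |
|---|---|---|---|---|
| 5% | 5% | 1.95 | 1.32 | 1.00 |
| 5% | 10% | 2.90 | 1.49 | 1.00 |
| 5% | 20% | 4.80 | 1.66 | 1.00 |
| 10% | 5% | 1.45 | 1.18 | 1.00 |
| 10% | 10% | 1.90 | 1.31 | 1.00 |
| 10% | 20% | 2.80 | 1.47 | 1.00 |
| 2% | 5% | 3.45 | 1.55 | 1.00 |
| 2% | 10% | 5.90 | 1.71 | 1.00 |
| 2% | 20% | 10.8 | 1.83 | 1.00 |

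If no prescribing takes place in these settings (f = 0) and g = 0, the ratio is also 1.00. These are risk ratios; the hazard ratio from the planned Cox model would differ somewhat.

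**Step 3. What the start point does.** If counting begins after rebound, or after any point by which treatment has been classified, the prescribing visits before that point drop out. So do the untreated group's early visits. Under no effect the ratio returns to 1.00, apart from prescriptions first issued after the start point.

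**The case against.** The strongest reply is that the Endpoints list in 9.4 is the natural place for an endpoint definition, and it counts only utilization after rebound. A prescription written soon after the first positive test would then precede the window. This stands as far as it goes, and it rules out saying that the problem exists whatever window is used. It does not settle the matter: Objective 2b says something else, nothing ranks the two, and 9.2.2.4 supports the index-date reading.

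A second reply is that rules for index-day and treatment-linked claims belong in the SAP, which is not shown. That is fair for the operational detail, whose absence is not the point here. The point is that the protocol itself states two start points, and a SAP faithful to Objective 2b would carry the problem forward.

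A reader might also infer that every treated participant scores an event, or that only the treated group is affected. The documents support neither. Office, telehealth or pharmacy contacts are not listed outcomes, and the documents do not say where Paxlovid was prescribed. Early ER and urgent care visits by untreated participants for the same illness count equally under Objective 2b. The distortion is therefore differential at most, and it vanishes if initial-care visits are equally common in both groups.

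Finally, the outcomes are exploratory, and section 9.6 describes a descriptive study with no a priori hypotheses. That limits the severity.

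**Conclusion.** The protocol gives two incompatible start points for the exploratory clinical outcomes. Under the Objective 2b wording, an ER or urgent care visit at which Paxlovid was prescribed is scored as an outcome. That can bias the comparison against Paxlovid wherever such visits are more common than initial-care visits among the untreated.

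The size cannot be determined from the documents. At an assumed 5% true risk and 5% to 20% of prescriptions written in these settings, the apparent ratio under no effect runs from 1.00 (equal initial-care visits) through 1.32 to 1.66 (half as many in the untreated) to 1.95 to 4.80 (none in the untreated). The last range is a worst case.

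It would go too far to say that the Paxlovid group will show a false safety signal: this depends on which definition is programmed and on the unknown visit frequencies. The protocol also calls these clinical outcomes, not adverse outcomes. Severity is low, because the primary endpoint is test-based and unaffected.

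**What to change.** Reconcile Exploratory Objective 2b and the Endpoints list in 9.4 to a single start point that falls after treatment status has been classified and applies identically in both groups. Two workable forms are:

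- a common fixed landmark day after index, with treatment status classified by that day; or
- the rebound date, with treatment classified by then. This suits Objective 2, which concerns rebounders. The window length should then be stated from rebound: a rebound on day 28 leaves only 30 − 28 = 2 days under the current 30-days-from-index limit.

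Count ER visits, urgent care visits, hospitalization and death only after that point. Do not delete the last visit before the fill in the treated group alone. With a common start point this is unnecessary, and otherwise it removes genuine visits from one group only. State how participants first treated after the start point are handled, since their prescribing visits would fall inside the window.

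The cost is a wording change in the protocol and SAP and one date filter, with no new data. The downside is that genuine early visits before the start point are not counted. Report them in a sensitivity analysis counted from index, labelled as including visits at which treatment was prescribed.
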